6.2.5 Definitions of dose limiting toxicities (DLTs)

A dose-limiting toxicity (DLT) is defined as an adverse event or abnormal laboratory value assessed as unrelated to disease progression, inter-current illness, or concomitant medications that meets any of the following criteria in [Table 6-3](#).

For the purpose of dose escalation decisions, only DLTs occurring during the first 6 weeks of study treatment will be necessarily considered and included in the BLRM.

[figure not shown]
Toxicity will be assessed using the NCI Common Terminology Criteria for Adverse Events, version 4.03 (evs.nci.nih.gov/ftp1/CTCAE) unless otherwise specified.

The investigator must notify the Sponsor immediately of any unexpected CTCAE grade ≥ 3 adverse events or laboratory abnormalities. Prior to enrolling patients into a higher dose level, CTCAE grade ≥ 2 adverse events will be reviewed for all patients at the current dose level.

For toxicities which, by definition, require a time-window in order to be defined as DLTs (grade 3 non-hematologic toxicity for ≥ 7 consecutive days), a subsequent visit and/or laboratory assessments must be scheduled accordingly. For example, if a grade 3 non-hematologic toxicity is observed, it must also be observed at least 7 days later, with no intervening lower grades, in order to qualify as a DLT.

Table 6-3 Criteria for defining dose-limiting toxicities

| TOXICITY | DLT CRITERIA |
|---|--|
| Hematologic | |
| Blood and lymphatic system disorders | Neutropenia CTCAE Grade 4* |
| | Febrile neutropenia CTCAE Grade ≥ 3 (ANC $< 1.0 \times 10^9/L$ + Fever ≥ 38.5 degrees C) |
| | Thrombocytopenia CTCAE Grade 4 (Platelets $< 25 \times 10^9/L$)* |
| | Hemorrhagic Event CTCAE Grade ≥ 2 |
| | Anemia CTCAE Grade 4 for ≥ 7 days despite PRBC transfusions |
| Non-Hematologic | |
| Gastrointestinal disorders | Vomiting CTCAE Grade ≥ 3 for > 7 days in duration |
| | Nausea CTCAE Grade 3 despite the use of anti-emetic therapy |
| Hepatic | Total bilirubin CTCAE Grade ≥ 3 , with Direct Bilirubin ≥ 0.5 mg/dL |
| | AST/SGOT or ALT/SGPT CTCAE Grade 3 for ≥ 5 consecutive days |
| | AST/SGOT or ALT/SGPT CTCAE Grade 4 |
| CK elevation | CTCAE Grade ≥ 3 |
| Other | Any CTCAE Grade 3 non-hematologic toxicity for ≥ 7 days Any CTCAE Grade 4 non-hematologic toxicity |
| CTCAE version 4.03 will be used for all grading. | |
| * In two consecutive assessments (the second assessment will be considered valid and final) | |

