Appropriate eligibility criteria and specific DLT definitions, as well as specific dose modification and stopping rules are included in this protocol.

Patients who experience a DLT will have their therapy with LDE225 and INC424 interrupted and will be followed as described in [Table 6-4](#). After recovery from the toxicity in question, if the Investigator believes that it is in the patient's best interest to resume therapy with LDE225 and INC424, the patient may resume therapy, only after consultation with the Sponsor, according to the guidelines described in [Section 6.3.1](#) and [Table 6-4](#).

However, the patient must be permanently discontinued from study medication and withdrawn from the study, if any of the following DLTs occur:

- any grade ≥ 3 hemorrhagic event
- grade 4 anemia for ≥ 7 consecutive days despite PRBC transfusions
- 2nd episode of grade ≥ 3 febrile neutropenia
- grade 3 renal toxicity for ≥ 7 consecutive days
- grade 4 renal toxicity
- grade 4 non-hematologic toxicity

If during the first 6 weeks a patient misses > 10 doses of LDE225 or > 20 doses of INC424, the patient will not be evaluable for DLTs. The patient can continue in the study, but another patient has to be enrolled at the same dose level in order to reach the required minimum number of patients in the cohort.

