6.3 Dose modifications

6.3.1 Dose modification and dose delay

For patients who do not tolerate the protocol-specified dosing schedule, dose adjustments are permitted in order to allow the patient to continue the study treatment. The following guidelines need to be applied. Any plan to deviate from these guidelines in view of patient safety must be discussed with the sponsor unless there is an urgent need for action.

All dose modifications should be based on the worst preceding toxicity as graded by the NCI Clinical Toxicity Criteria (NCI-CTCAE version 4.03). If study treatment is held due to toxicity, scheduled visits and all assessments as described in [Table 7-1](#) should continue as scheduled, except without dosing. Dose modification guidelines are described in [Table 6-4](#).

If an adverse event is clearly associated to one of study drugs, the dose adjustment directed for that study drug will be followed; however, if the causality is not clear, then it may be necessary to adjust both study drugs. Dosing adjustments will be discussed with the sponsor.

If a patient experiences a DLT then treatment with LDE225 plus INC424 must be stopped and the patient may be discontinued from the study. However, following resolution of the DLT to CTCAE grade 1 or to the patient's baseline value, the patient may continue to receive study treatment at a reduced combination dose level, if appropriate, at the discretion of the investigator and after discussion with the Sponsor.

For each patient, a maximum of 2 dose reductions will be allowed, after which the patient will be required to discontinue study treatment. If the same toxicity returns after re-initiation of treatment at the same dose level, the second re-initiation must resume at a lower dose level. The patient must also discontinue study treatment if, after the treatment is resumed at the lower dose level, the same toxicity recurs with the same or worse severity (except for thrombocytopenia, anemia and neutropenia).

Dose level (-1) is the lowest acceptable dosing level for a patient participating in the study. If a patient cannot tolerate dose level (-1), then study treatment must be discontinued and the patient must be withdrawn from the study. However, if patients in Cohort 1 experience thrombocytopenic DLTs then patients in dose level (-1) will receive INC424 5mg BID and LDE225 200 mg QD.

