| Asymptomatic or Symptomatic CK elevation | |
| Grade 3 or 4 without renal impairment [Grade 3 (CK elevation $>5 \times$ ULN - $10 \times$ ULN)] [Grade or 4 (CK elevation $>10 \times$ ULN)] | 
 Interrupt treatment and monitor CK levels weekly until resolution to baseline level. Monitor muscle symptoms for changes until resolution to baseline. Check renal function (serum creatinine) regularly and ensure that patient is adequately hydrated. If renal function is not impaired (normal serum creatinine) and CK resolves to baseline level, consider resuming treatment at a reduced dose. CK levels should be measured weekly for 2 months after re-administration of sonidegib and monthly thereafter. |
| Grade 3 or 4 with renal impairment | 
 Interrupt treatment and monitor CK levels weekly until resolution to baseline level. Monitor muscle symptoms for changes until resolution to baseline. If renal function is impaired ($\geq 50\%$ above the baseline level), interrupt treatment. Ensure patient is adequately hydrated and evaluate other secondary causes. Continue monitoring of CK and creatinine levels weekly. If CK levels return to baseline level and creatinine levels return to baseline, consider resuming treatment at the reduced dose otherwise discontinue treatment permanently. |

Table 6-6 Dose restart guidelines and allowed maximum doses for patients who have previously interrupted dose for grade 4 thrombocytopenia and grade 4 neutropenia

[figure not shown]
| Current PLT Count | ▼ Dose Restart or Dose Increase Guidelines ▼ | |
|-----------------------------------|--|--------------------------------|
| | INC424 | LDE 225 |
| < 50 x10 ⁹ /L | Continue to hold | Continue to hold |
| 50 to < 75 x10 ⁹ /L | Restart at 5 mg BID for at least 14 days If stable, may increase to 10 mg BID or original dose (whichever is lower) | Restart at original dose level |
| 75 to < 100 x10 ⁹ /L | Restart at 10 mg BID for at least 14 days If stable, may increase to 15 mg BID or original dose, (whichever is lower) | Restart at original dose level |
| 100 to < 125 x10 ⁹ /L | Restart at original dose | Restart at original dose level |
| ≥ 125 x10 ⁹ /L | Restart at original dose | Restart at original dose level |
| Current ANC Level | ▼ Dose Restart or Dose Increase Guidelines ▼ | |
| < 0.5 x10 ⁹ /L | Continue to hold | Continue to hold |

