7.1.3 Discontinuation of Study Treatment

Patients may voluntarily discontinue from study treatment for any reason at any time. If a patient decides to discontinue from the study treatment, the investigator must make every effort (e.g., telephone, e-mail, letter) to determine the primary reason for this decision and record this information in the patient's chart and on the appropriate eCRF pages. Patients may be considered withdrawn if they state an intention to withdraw, fail to return for visits, or become lost to follow-up for any other reason.

The investigator should discontinue study treatment for a given patient if he/she believes that continuation would be detrimental to the patient's well-being.

Study treatment must be discontinued under the following circumstances:

- Emergence of the following adverse events:
 - Grade 3 or 4 hemorrhagic event of any kind
 - Grade 3 renal toxicity for ≥ 7 consecutive days
 - Grade 4 renal toxicity
 - Grade 4 non-hematologic toxicity
 - Second occurrence of QTcF > 500 ms (\geq Grade 3) or > 60 ms change from baseline on at least two separate ECGs
 - Patient requires or undergoes splenic irradiation
 - Patient requires or undergoes splenectomy
- Any of the following laboratory abnormalities:
 - Grade 4 anemia for ≥ 7 consecutive days despite PRBC transfusions
 - Febrile neutropenia (Grade ≥ 3) (ANC $< 1.0 \times 10^9/L$, with a single temperature of ≥ 38.3 °C or a sustained temperature of ≥ 38 °C for more than one hour)
 - Grade 3 or 4 serum creatinine
 - Bilirubin $> 10.0 \times ULN$
 - Grade 3 or 4 asymptomatic or symptomatic CK elevation with renal function impairment in which CK and creatinine levels do not return to baseline after interrupting treatment
- Pregnancy

- The following deviations from the prescribed dose regimen for LDE225 and INC424:
 - Interruption of study treatment for > 21 days, regardless of reason, from the intended day of the next scheduled dose. However, if the patient is obtaining clinical benefit in terms of response, the patient may continue treatment at the same or at a reduced dose following discussion between the investigator and Novartis.
 - If after 2 dose reductions and after the treatment has resumed at the lower dose, the same toxicity recurs with the same or worse severity (except for thrombocytopenia, anemia, and neutropenia)

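### The blanket Grade 4 non-hematologic stop in Protocol 6.2.5 conflicts with the restart rules for Grade 4 CK (Table 6-5) and Grade 4 AST/ALT (Table 6-4), and 7.1.3 repeats the stop unqualified

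*Protocol*

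**What the plan says.** **The stop.** Protocol 6.2.5 first gives a general rule: after recovery from a DLT, "the patient may resume therapy, only after consultation with the Sponsor". It then overrides that rule for a list of events: "However, the patient must be permanently discontinued from study medication and withdrawn from the study, if any of the following DLTs occur". One item on the list is "grade 4 non-hematologic toxicity", with no exception.

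**The classification.** Table 6-3, in the same section, places CK elevation of Grade 3 or higher and AST/ALT of Grade 4 under its non-hematologic heading, each in its own row. A separate residual row, labelled Other, contains "Any CTCAE Grade 4 non-hematologic toxicity".

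**The restart.** Section 6.3.1 sends all muscle toxicity to Table 6-5, DLT or not. For Grade 3 or 4 CK without renal impairment, Table 6-5 says: "If renal function is not impaired (normal serum creatinine) and CK resolves to baseline level, consider resuming treatment at a reduced dose". With renal impairment it says: "If CK levels return to baseline level and creatinine levels return to baseline, consider resuming treatment at the reduced dose otherwise discontinue treatment permanently". For Grade 4 AST/ALT without bilirubin above 2 x ULN, Table 6-4 holds both drugs until recovery, then cuts INC424 by 5 mg BID and LDE225 by one dose level. The Grade 4 discontinuation row of Table 6-4 applies only to other non-hematological events. For DLTs generally, 6.3.1 allows continuation "at a reduced combination dose level, if appropriate, at the discretion of the investigator and after discussion with the Sponsor".

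**The discontinuation section.** Protocol 7.1.3 lists "Grade 4 non-hematologic toxicity" as a mandatory stop, again unqualified. Separately, it requires a stop for Grade 3 or 4 CK with renal impairment when CK and creatinine fail to return to baseline.

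**The concern.** A patient with Grade 4 CK whose CK is back at baseline and whose renal function is normal or recovered must be stopped and withdrawn under 6.2.5, but may be restarted at a reduced dose under Table 6-5. A patient with Grade 4 AST/ALT and no bilirubin rise must be stopped under 6.2.5, but is held and then reduced under Table 6-4.

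Stopping one drug permanently ends both (4.3.1). A patient who drops out before Week 24 counts as a non-responder (SAP 3.5.3). In the other direction, a restart that follows the tables breaches a rule written as mandatory, and Section 12 allows no authorized deviations.

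**Working it through.** The check is mainly a comparison of texts, followed by arithmetic on Table 1-2 to size the effect. The plan states no figure of its own to reproduce beyond the Table 1-2 totals.

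**1. Does the 6.2.5 bullet reach CK and AST/ALT?** Yes. The section defines a DLT to include abnormal laboratory values, and Table 6-3 puts both toxicities under the non-hematologic heading. The bullet lacks the Other qualifier found in Tables 6-3 and 6-4.

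**2. Do the tables reach DLTs?** Yes. The 6.3.1 routing sentence for muscle toxicity covers DLTs expressly. For AST/ALT, 6.2.5 itself refers DLT restarts to Table 6-4.

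**3. Does 7.1.3 settle it?** No. It holds two stop criteria of different breadth and no restart rule. The narrower CK stop implies that recovered Grade 4 CK need not end treatment, since the broad bullet would already have stopped every Grade 4 case. It does not say so.

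**4. Table 1-2 totals (study X2101, LDE225 alone).**
- Treated: 6+6+5+26+11+9+10+14+8+8 = 103
- Grade 3: 1+1+1+1 = 4
- Grade 4: 1+1+3+3+1+1+5 = 15
- Total: 4 + 15 = 19. All match the table.

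**5. Grade 4 CK at doses relevant here.** Limits are exact (Clopper-Pearson) 95%. For zero events in n, the upper limit is 1 − 0.025^(1/n).
- At or below 400 mg QD (the confirmed RPIID uses 400 mg): 6+6+5 = 17 treated, 0 events; upper limit 1 − 0.025^(1/17) = 19.5%
- 800 mg QD: 1/26 = 3.8%
- QD doses up to 800 mg: 17+26 = 43 treated, 1 event = 2.3% (0.06% to 12.3%)
- 1500 mg QD, 3000 mg QD and 750 mg BID, all outside this trial's range: 9+10+8 = 27 treated, 3+3+5 = 11 of the 15 Grade 4 events

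**6. Expected number among the 20 Stage 1 patients.** The documents give no CK rate for the combination, so these rates are assumptions:
- Observed rate at or below 400 mg: 20 × 0/17 = 0
- Rate up to 800 mg: 20 × 1/43 = 0.5
- 800 mg rate: 20 × 1/26 = 0.8
- Upper limit at or below 400 mg: 20 × 0.195 = 3.9

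Each patient is at most 1/20 = 5 percentage points of the Stage 1 response rate.

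**7. The 21-day limit.** Sections 6.3.1 and 7.1.3 end treatment after an interruption of more than 21 days, unless the patient is benefiting in terms of response and continuation is discussed with the sponsor. Section 1.4.1.2.1 reports that X2101 DLTs resolved in 4 to 8 weeks, i.e. 28 to 56 days. Both ends exceed 21 days, so the figures in step 6 are ceilings on the patients for whom the choice of rule changes the outcome.

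**8. Restart experience.** Of the 19 X2101 patients with Grade 3/4 CK, 8 resumed at reduced doses with no further Grade 3/4 elevation (0/8; upper limit 1 − 0.025^(1/8) = 37%). Only 4 of the 19 were Grade 3, so at least 8 − 4 = 4 of the 8 resumed after Grade 4. The literal 6.2.5 rule would forbid those restarts.

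**The case against.** **The specific rule governs.** The 6.3.1 routing sentence, the CK stop in 7.1.3 and the Other rows of Tables 6-3 and 6-4 all point to the specific text. This is probably the intent, and the fix adopts it. But it is never stated against the mandatory list in 6.2.5, which expressly overrides the restart sentence before it. AST/ALT has no routing sentence like the one for muscle toxicity.

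**Obeying the stricter rule satisfies everything.** Table 6-5 is headed as a recommendation and only asks sites to consider a restart, so stopping breaches nothing for CK. True, but the Grade 4 restart text in both tables would then never apply to a DLT.

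**Sponsor consultation prevents divergence.** It limits differences between sites. It does not tell the sponsor which rule to apply.

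**CK is a laboratory finding, not an adverse event, in 7.1.3.** This fails: 8.1.2.1 treats a laboratory abnormality that requires a protocol dose hold as an adverse event.

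**A reader might infer that 7.1.3 contradicts itself.** The documents do not support that. It lists stops only, and its CK bullet also covers Grade 3, so the two criteria overlap without contradiction. The permission to restart is implied there, not written.

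**The practical effect is small.** This stands. Grade 4 CK was 0/17 at or below 400 mg QD, the 21-day limit would often decide the outcome first, and 6.2.5 sits among the dose-escalation guidelines, so for Phase II the exposure runs mainly through 7.1.3. All 20 Stage 1 patients had been treated by February 2015, and Stage 2 was not opened (SAP 1.1). For AST/ALT the documents give no separate Grade 4 rate; Table 1-3 shows no related Grade 3/4 event among 26 patients at 800 mg QD.

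**Conclusion.** The conflict is real in 6.2.5 for Grade 4 CK, and for Grade 4 AST/ALT without bilirubin above 2 x ULN. Section 7.1.3 repeats the unqualified stop beside a narrower CK stop and leaves the matter open. It should be corrected as a patient-management rule that is wrong as written.

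Its size is small. If single-agent CK rates carry over to the combination, the expected number among 20 Stage 1 patients runs from 0 to 0.8, with 3.9 at the upper confidence limit, before the 21-day limit is applied. How many would recover within 21 days or qualify for the response-based exception cannot be derived from the documents.

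Two further inferences are not supported. The dose-escalation result is not in doubt: Grade 4 CK and Grade 4 AST/ALT are DLTs under either reading, so DLT counting and the BLRM are unchanged. Nor do the documents show that the Stage 1 response rate was distorted; 5 percentage points per affected patient is a ceiling, not an estimate.

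**What to change.** In 6.2.5 and 7.1.3, change the bullet to: *other grade 4 non-hematologic toxicity (except CK elevation, managed per Table 6-5, and AST/ALT elevation without bilirubin > 2 x ULN, managed per Table 6-4)*.

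Keep the CK stop for unresolved renal impairment, the sponsor consultation before restart and the 21-day limit. If the sponsor intends a permanent stop for Grade 4 AST/ALT, correct the Table 6-4 row instead; the documents offer no restart data for that toxicity.

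The cost is one phrase in each of two sections at the next amendment. It adds no visits, assessments or patients and leaves the DLT definitions as they are. The change still matters for patients on treatment: at Amendment 2, 50 − 14 = 36 treated patients had not discontinued, and treatment may continue into the extension phase.

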5.3 Exclusion criteria

Patients eligible for this study must not meet **any** of the following criteria:

1. Previous therapy with JAK inhibitors.
2. Previous therapy with a Smo inhibitor.
3. Patients with inadequate organ function as demonstrated by:

- encephalopathy grade 1 or more, as per West Haven Criteria ([Ferenci 2002](#), [Appendix 6](#)),
 - known hepatocellular disease (e.g. active hepatitis or cirrhosis),
 - Total bilirubin ≥ 2 x upper limit of normal (ULN) range of values, unless due to elevated indirect bilirubin (e.g. Gilbert's syndrome or hemolysis),
 - alanine aminotransferase (ALT) > 3 ULN,
 - MDRD eGFR < 30 mL/min/1.73m² or on dialysis ([Appendix 5](#)),
 - Creatine phosphokinase (CPK) > 1.5 x ULN.
4. Patient has impaired cardiac function or clinically significant heart disease, including any one of the following:
 - Clinically significant heart disease (e.g., congestive heart failure, uncontrolled hypertension, history of labile hypertension, or history of poor compliance with an antihypertensive regimen),
 - QTc interval corrected for heart rate using Fridericia's formula (QTcF) > 450 msec for males and > 470 msec for females on the screening ECG,
 - A past medical history of clinically significant ECG abnormalities or a family history of prolonged QT-interval syndrome,
 - Angina pectoris within 3 months before first dose of study treatment,
 - Acute myocardial infarction within 3 months before first dose of study treatment.
 5. Patient has evidence of an active malignancy, with the exception of controlled prostate cancer, basal cell or squamous cell carcinoma of the skin, or carcinoma "in situ" of the cervix or breast and has been disease-free for more than 3 years.
 6. Patients with acute bacterial infections requiring antibiotic therapy should delay screening/enrollment until the course of antibiotics has been completed.
 7. Patient is currently on medications that interfere with coagulation (including warfarin) or platelet function. Low dose aspirin (up to 150 mg per day) and low molecular weight heparin (LMWH) are allowed.
 8. Patient has impairment of gastrointestinal (GI) function or GI disease that may significantly alter the absorption of INC424 or LDE225 (e.g., uncontrolled nausea, vomiting, diarrhea; malabsorption syndrome; small bowel resection).
 9. Patient had major surgery within 2 weeks of initiation of study medications.
 10. Patients who have had splenic irradiation within 12 months prior to Screening.

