If a patient requires a dose delay from either study drug of > 21 days due to an LDE225 or INC424 related toxicity, then the patient must be discontinued from the study; however, if the patient is obtaining clinical benefit in terms of response, the patient may continue treatment at the same or at a reduced dose following discussion between the investigator and Novartis. All patients will be followed for AEs and SAEs for 30 days following the last dose of LDE225 and/or INC424.

Dose modifications for toxicities occurring during the DLT-definition period (6 weeks or 42 days) will not be allowed unless the toxicity qualifies as a DLT. After a toxicity has been characterized as a DLT, a patient can resume therapy with a reduced treatment dose according to the guidelines provided in [Section 6.2.5.1](#).

If the administration of study treatment was interrupted for reasons other than toxicity, then treatment with LDE225 and INC424 may be resumed at the same dose.

Patients who experience muscle toxicity, regardless of whether the toxicity meets the criteria described for a DLT, should be followed according to the dosing modifications for LDE225 as per [Table 6-5](#).

Patients who experience hematologic, renal, or hepatic toxicities should receive follow up evaluations as outlined in [Table 6-7](#).

All interruptions or changes to study drug administration must be recorded on the Dosage and Administration Record eCRF.

[figure not shown]

Table 6-4 Criteria for interruption and re-initiation of INC424 and LDE225 treatment

| | |
|--|---|
| Dose modifications for toxicities occurring during the DLT-definition period (6 weeks or 42 days), and considered as treatment-related, will not be allowed until the toxicity qualifies as a DLT. | |
| Worst toxicity (CTCAE 4.03 Grade) | Dose Modifications for INC424 and LDE225 |
| HEMATOLOGICAL | |
| Neutropenia (ANC) (for 2 consecutive assessments within 48 hrs except febrile neutropenia) | |
| Grade 1 (ANC < LLN - $1.5 \times 10^9/L$) Grade 2 (ANC < $1.5 - 1.0 \times 10^9/L$) Grade 3 (ANC < $1.0 - 0.5 \times 10^9/L$) | INC424: Maintain dose level LDE225: Maintain dose level |
| Grade 4 (ANC < $0.5 \times 10^9/L$) | INC424: Hold dose until resolved to \leq grade 1, then maintain dose level LDE225: Hold dose until resolved to \leq grade 1, then maintain dose level |

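### Table 6-5 judges renal status after grade 3 or 4 CK elevation against two different references, so some patients fit both rows and others neither when restart or permanent stop is decided

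*Protocol*

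**What the plan says.** Protocol section 6.3.1 sends every patient with muscle toxicity, whether or not it is a DLT, to Table 6-5: they "should be followed according to the dosing modifications for LDE225 as per" that table. For grade 3 or 4 CK elevation the table has two rows, and both begin by interrupting treatment.

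- **Row without renal impairment:** "If renal function is not impaired (normal serum creatinine) and CK resolves to baseline level, consider resuming treatment at a reduced dose". The bracket ties absence of impairment to the laboratory normal range.
- **Row with renal impairment:** "If renal function is impaired ($\geq 50\%$ above the baseline level), interrupt treatment". Later in the same row: "If CK levels return to baseline level and creatinine levels return to baseline, consider resuming treatment at the reduced dose otherwise discontinue treatment permanently". The 50% clause does not name what is measured; the sentences after it refer to creatinine.

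Section 7.1.3 lists among the mandatory reasons to stop treatment: "Grade 3 or 4 asymptomatic or symptomatic CK elevation with renal function impairment in which CK and creatinine levels do not return to baseline" after interruption. It does not say what counts as renal function impairment. The same list separately contains "Grade 4 non-hematologic toxicity".

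On eligibility, exclusion criterion 3 in section 5.3 rejects on renal grounds only "MDRD eGFR < 30 mL/min/1.73m² or on dialysis". A normal creatinine at baseline is not required.

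**The concern.** The two rows are meant to divide patients with grade 3 or 4 CK elevation into two groups, but one is defined by the normal range and the other by change from the patient's own baseline. Nothing makes these complementary.

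The row matters because it carries the decision. CK elevation was the dose-limiting toxicity of single-agent LDE225 (section 1.4.1.2.1), and grade 3 or higher CK elevation is a DLT here (Table 6-3). Under section 4.3.1, permanently stopping one drug means stopping the other. A patient who fits both rows can be considered for restart under one and must stop permanently under the other, so two sites could treat the same laboratory values differently and each cite the protocol. A patient who fits neither row has no CK-specific answer in the table.

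**Working it through.** There is no stated figure to reproduce; this is a check of two definitions.

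**Notation.** b = baseline creatinine / ULN; c = current creatinine / ULN. The 50% clause is read as referring to creatinine.

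- Row without impairment applies if c ≤ 1.
- Row with impairment applies if c ≥ 1.5b.

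**Overlap:** both hold when 1.5b ≤ c ≤ 1, which needs b < 2/3 for a range of values.
**Gap:** neither holds when 1 < c < 1.5b, which needs b > 2/3.
**Meeting point:** 1.5b = 1, so b = 2/3.

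| b (× ULN) | 1.5b | Result |
|---|---|---|
| 0.5 | 0.75 | both rows for c from 0.75 to 1.00 |
| 0.6 | 0.90 | both rows for c from 0.90 to 1.00 |
| 0.8 | 1.20 | neither row for c between 1.00 and 1.20 |
| 1.0 | 1.50 | neither row for c between 1.00 and 1.50 |
| 1.2 | 1.80 | neither row for c between 1.00 and 1.80 |

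The result does not depend on the value of the ULN, which the documents do not give.

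**Consequence in the overlap.** Take b = 0.5, c = 0.8 and CK back at baseline. Creatinine is within normal, so the first row lets restart be considered. It is also 0.8/0.5 = 1.6 times baseline, so the second row applies, and unless creatinine returns to baseline it directs permanent discontinuation.

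**Consequence in the gap.** Take b = 0.8 and c = 1.1. Creatinine is above normal but only 1.1/0.8 = 1.375 times baseline. Neither row's test is met. This patient started with a normal creatinine, so the gap is not confined to chronic renal disease.

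**Stable raised baseline.** If b > 1 and creatinine does not change, then c = b and 1 < c < 1.5b always holds. Such a patient is in the gap with no renal change at all.

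**Can such patients enrol?** Appendix 5 gives eGFR = 170 × creatinine^-0.999 × age^-0.176 × urea nitrogen^-0.170 × albumin^0.318 (× 0.762 if female; × 1.180 if black, not applied here). The inputs below are assumptions. With age 65, urea nitrogen 20 mg/dL, albumin 4.0 g/dL and creatinine 1.6 mg/dL, eGFR is 47.6 for a man and 47.6 × 0.762 = 36.3 for a woman. For three input sets (age 60 to 75, urea nitrogen 18 to 30, albumin 3.8 to 4.0) and both sexes, the range at 1.6 mg/dL is 32.5 to 49.2, all above the limit of 30. At 2.0 mg/dL it is 26.0 to 39.3, so some would be excluded. A creatinine of 1.6 mg/dL is above normal for any ULN below 1.6: b = 1.6/1.2 = 1.33 at an assumed ULN of 1.2, and 1.6/1.4 = 1.14 at 1.4.

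**Does another passage settle it?** Table 6-4 sets creatinine rules by multiples of ULN: maintain below 2, hold at 2 to 3, discontinue above 3. These apply whatever the CK, but they do not define renal impairment for Table 6-5 and do not govern restart after a CK interruption. For b up to 2/1.5 = 1.33, the whole gap lies below 2 × ULN, in the maintain row. Section 7.1.3 repeats the stop rule and leaves the key term undefined.

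**The case against.** The strongest reply is that the rules are surrounded by safeguards. Both rows interrupt treatment, and restart is only to be considered. The title of Table 6-5 presents its content as recommendations. Grade 3 or higher CK elevation is a DLT, and sections 6.2.5 and 6.3.1 allow therapy to resume after a DLT only with sponsor consultation and investigator judgement. In the overlap, a reader may take the mandatory rule in 7.1.3 as prevailing over a row that only permits consideration.

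Much of this stands, and it limits the harm. It does not remove the contradiction. Consultation says who decides, not by what rule. Section 7.1.3 cannot break the tie, because whether it applies depends on the definition in dispute, and no order of precedence is stated.

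Several stronger readings are tempting, and the documents do not support them:

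- **That the first row allows restart on CK alone.** It also requires a normal creatinine. The difference is between a normal value and a return to baseline.
- **That patients with chronic renal impairment have no instruction.** The Table 6-4 creatinine rows and sponsor consultation still apply. What is missing is a CK-specific restart or stop rule.
- **That the single-agent CK rates measure the problem.** The 7.7% (800 mg QD) and 18.4% (all doses) in Table 1-3 are all grade 3/4 CK elevations, not cases with ambiguous renal status. Section 1.4.1.2.1 reports no renal impairment from this toxicity, and Table 1-2 shows 0 of 5 at 400 mg QD, the LDE225 dose in the confirmed RPIID. Of the 19 events, 15 were grade 4, leaving 4/103 = 3.9% at grade 3.
- **That a permanent stop makes the patient a non-responder.** SAP section 3.5.3 does this only for dropout, or a missing assessment, at the Week 24 or Week 48 visit respectively. A stop after Week 24 does not itself change the Week 24 result.

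**Conclusion.** The inconsistency is real and should be corrected. The two Grade 3/4 rows of Table 6-5 are complementary only when baseline creatinine is exactly 2/3 of ULN. Below that they overlap, with conflicting outcomes; above it they leave a gap, which includes eligible patients whose stable baseline is above normal.

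The scope is narrow. The conflict concerns restart versus permanent stop, not the initial interruption. It stands mainly for grade 3 CK elevation, because grade 4 also falls under the separate stop rule for grade 4 non-hematologic toxicity. How that rule fits with Table 6-5 is a different question. The number of patients affected is unknown, since the documents give no distribution of baseline creatinine, and it is probably small. No effect on power or on the decision rule has been shown; the effect on the primary endpoint is conditional, as set out above.

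The conclusion assumes that the 50% clause refers to creatinine. The eligibility example also depends on the assumed age, urea nitrogen, albumin and ULN; the overlap and the gap do not.

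**What to change.** Reconcile the two Grade 3/4 rows of Table 6-5 and the matching item in section 7.1.3 to a single definition of renal impairment. Name the analyte, use one reference value, and word the rows so that every patient with grade 3 or 4 CK elevation falls in exactly one, including those whose baseline creatinine is above normal. Which reference is right is a clinical decision for the sponsor, and this review does not propose one.

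The cost is a wording change in two places, made by protocol amendment. No new data are needed: creatinine is already in the chemistry panel (Table 7-6).
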